# 12.3.3. Exploratory endpoint

Molecular and pathological changes in response to atezolizumab +/- radiotherapy

# 12.4. Statistical analysis plan

#### **Primary endpoint**

Objective response rate (CR [complete response] + PR [partial response]) at 9 weeks after start of study treatment will be compared between the two trial arms using a chi-squared test or Fisher's exact test, as appropriate, and an estimate of the difference in proportions of responders calculated with a 95% confidence interval.

Blinded central review of objective responses will be conducted retrospectively.

A supplementary analysis will consider objective response rate at 9 weeks as above, but incorporating the (planned) radiotherapy site within the RECIST v1.1 assessment (where it met the criteria for a RECIST v1.1 target lesion) to assess the impact of excluding this lesion in the principal analysis.

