#### 8. TRIAL ASSESSMENTS

## 8.1. Screening assessments

The following assessments should be conducted within 28 days prior to randomisation unless otherwise indicated:

- Physical examination
- Medical history
- ECOG performance status assessment
- Full blood count, urea and electrolytes, amylase and liver function assessment
- Thyroid function assessment
- Serology (HIV, hepatitis B, hepatitis C) (within 12 months prior to randomisation)
- Concomitant medication assessment
- Adverse event assessment (CTCAE v5)
- CT chest abdomen pelvis (CAP) and RECIST v1.1 assessment\*
- QoL sub-study questionnaire (if participating): EORTC QLQ-C30 and EQ-5D-5L

\*The planned site of radiotherapy should not be used for RECIST v1.1 assessment (as either a target or non-target lesion), but measurement of this lesion should be recorded on the dedicated eCRF.

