## 9.1.1. Radiotherapy target selection

It is recommended that the lesion selected to receive radiotherapy:

- Should be a lesion that is progressing, if applicable
- May be RECIST v1.1 measurable or non-measurable e.g. bone or bladder
- Should be 1.5cm to 10cm in diameter. If not available a larger lesion can be selected and partially treated
- Should not have been previously irradiated

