#### 9.1.4. Target volume definition

The Clinical Target Volume (CTV) will be the investigator defined gross tumour volume (GTV) plus 0.5 cm. An additional 0.5 - 1.0cm margin will be added to the CTV to form the planning target volume (PTV). The PTV should have a minimum diameter of 3.5 cm and not exceed a maximum diameter of 12 cm. The treated target site may be RECIST measurable or non-measurable.

Ideally, the whole lesion will be irradiated however partial irradiation is permitted in order not to exceed the maximum allowable PTV.

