#### A1.1 Evaluation of measurable and non-measurable lesions

- Measurable disease the presence of at least one measurable lesion. If the measurable disease is restricted to a solitary lesion, its neoplastic nature should be confirmed by cytology / histology.
- Measurable lesions lesions that can be accurately measured in at least one dimension with the longest diameter  $\geq$  20 mm by chest X-ray, or  $\geq$  10 mm by CT/MRI scan or clinical exam.
- Lytic bone lesions or mixed lytic-blastic lesions, with identifiable soft tissue components, that
  can be evaluated by cross sectional imaging techniques such as CT or MRI can be considered
  as measurable lesions if the soft tissue component meets the definition of measurability
  described above.
- 'Cystic lesions' thought to represent cystic metastases can be considered as measurable lesions, if they meet the definition of measurability described above. However, if non-cystic lesions are present in the same patient, these are preferred for selection as target lesions.
- Malignant lymph nodes must be ≥15 mm in the short axis when assessed by CT scan to be considered measurable.
- Non-measurable lesions all other lesions, including small lesions and malignant lymph nodes
  (longest diameter <10 mm, or pathological lymph nodes with ≥10 to <15 mm short axis) i.e.,
  leptomeningeal disease, ascites, pleural/pericardial effusion, inflammatory breast disease,
  lymphangitis cutis/pulmonis, cystic lesions, blastic bone lesions and also abdominal masses
  that are not confirmed and followed by imaging techniques.

- Tumour lesions situated in a previously irradiated area, or in an area subjected to other locoregional therapy, are usually not considered measurable unless there has been demonstrated progression in the lesion.
- The utilisation of endoscopy and laparoscopy for objective tumour evaluation is not advised.
   The utilisation of such techniques should be restricted to confirming complete pathological response when biopsies are obtained.

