# A1.2 Baseline documentation of target and non-target lesions

- Measurable lesions up to a maximum of 2 lesions per organ and 5 lesions in total representative of all involved organs should be identified as target lesions and recorded and measured at baseline.
- Target lesions should be selected on the basis of their size (lesions with the longest diameter), be representative of all involved organs, but in addition should be those that lend themselves to reproducible repeated measurements. It may be the case that, on occasion, the largest lesion does not lend itself to reproducible measurement in which circumstance the next largest lesion which can be measured reproducibly should be selected.
- All measurements should be taken and recorded in metric notation, using a ruler or calipers.
   All screening evaluations should be performed as closely as possible to the beginning of treatment and never more than 4 weeks before the beginning of treatment.

- The same method of assessment and the same technique should be used to characterise each identified and reported lesion at baseline and during follow up.
- A sum of the longest diameters (LD) for all target lesions will be calculated and reported as the baseline sum of LD. The baseline sum LD will be used as reference by which to characterise the objective tumour.
- All other lesions (or sites of disease) should be identified as non-target lesions and should also be recorded at baseline. Measurements of these lesions are not required, but the presence or absence of each should be noted throughout follow up. In addition, it is possible to record multiple non-target lesions involving the same organ as a single item on the case record form (e.g. 'multiple enlarged pelvic lymph nodes' or 'multiple liver metastases').

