# A1.6 Evaluation of overall response

The table below provides a summary of the overall response calculation at each time point.

Target lesions	Non-target lesions	New lesions	Overall response
CR	CR	No	CR
CR	Incomplete response/SD	No	PR
CR	Not-evaluated*	No	PR
PR	Non-PD or not all evaluated	No	PR
SD	Non-PD or not all evaluated	No	SD
Not all evaluated	Non-PD	No	Not evaluable
PD	Any	Yes or No	PD
Any	PD	Yes or No	PD
Any	Any	Yes	PD

\* When no imaging/measurement is done at all at a particular time point, the patient is not evaluable (NE) at that time point. If only a subset of lesion measurements are made at an assessment, usually the case is also considered NE at that time point, unless a convincing argument can be made that the contribution of the individual missing lesion(s) would not change the assigned time point response.

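### The supplementary response analysis restores the planned radiotherapy site only as a target lesion, so it misses progression of sites that could only be non-target lesions

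*Protocol*

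**What the plan says.** **The exclusion.** Section 8.1 says the planned site "should not be used for RECIST v1.1 assessment (as either a target or non-target lesion"). Footnote 4 of section 8.10 repeats this for later scans, and sections 8.4, 9.1 and A1 apply the exclusion whether or not radiotherapy is allocated. What is asked for instead is a measurement of the lesion on a dedicated eCRF (8.1, 8.4, 8.10).

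**The sites allowed.** Section 9.1.1 says of the chosen lesion: "May be RECIST v1.1 measurable or non-measurable e.g. bone or bladder". Section 9.1.4 agrees: "The treated target site may be RECIST measurable or non-measurable". Section 9.1.1 also recommends choosing a progressing lesion where there is one.

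**The check.** The supplementary analysis in section 12.4 repeats the week 9 comparison with the planned site included "where it met the criteria for a RECIST v1.1 target lesion) to assess the impact of excluding this lesion in the principal analysis".

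**The response rules.** A1.2 sets the target set as "Measurable lesions up to a maximum of 2 lesions per organ and 5 lesions in total"; all other disease is non-target. Under A1.5 and A1.6, unequivocal progression of non-target disease makes the overall response progressive disease whatever the targets show.

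**The concern.** The exclusion removes the site from two roles, and the check gives it back in one. If the planned site is not a target lesion, nothing is restored, and that patient has the same response in both analyses whatever happened to the lesion.

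The gap is not empty. Non-measurable sites are expressly allowed, a progressing lesion is the recommended choice, and disease status (stable or progressive) is a balancing factor in section 12.2, so patients with progressing disease are expected. In the control arm that lesion receives no trial radiotherapy. A control patient with a partial response elsewhere and unequivocal progression at a non-measurable planned site is counted as a responder in both analyses.

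What is at stake is how the supplementary result is read. Close agreement between the two analyses would be taken as evidence that excluding the lesion did not matter, when for some patients agreement was guaranteed in advance.

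**Working it through.** **1. What changes if the planned site is added as a non-target lesion.** The A1.6 rules were applied to every combination of target status (CR, PR, SD, PD), status of the other non-target disease (CR, persisting, PD), new lesion (no, yes) and status of the planned site (CR, persisting, PD): 4 × 3 × 2 × 3 = 72 combinations. Response status (CR or PR against neither) changes in 4:

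| Targets | Other non-target | New lesion | Planned site | Without site | With site |
|---|---|---|---|---|---|
| CR | CR | no | PD | CR | PD |
| CR | persisting | no | PD | PR | PD |
| PR | CR | no | PD | PR | PD |
| PR | persisting | no | PD | PR | PD |

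All four turn a responder into a non-responder. No combination creates a responder. A planned site that merely persists can turn CR into PR, which is still a response. The A1.6 rows for unevaluated lesions were not enumerated, but an unevaluated non-target lesion leaves CR or PR targets at PR, so it removes no response.

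**2. Size in the control arm.** Inputs from section 12.1: 92 evaluable patients, so 92 / 2 = 46 per arm, and a control response rate of 15%. The plan's figure of 92 is consistent with its stated design: a fixed design for 15% against 30% at one-sided 0.2 and 80% power needs 44 per arm (88), and with the interim look at 23 per arm and boundaries of 0 and 0.68, exact power at 46 per arm is 79.5%.

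Expected control responders: 46 × 0.15 = 6.9.

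Two inputs are not in the protocol and are assumed: *f*, the share of patients whose planned site is non-measurable (10 to 50%), and *q*, the chance of unequivocal progression of that site by week 9 in a control patient who responds elsewhere (5 to 40%).

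Control responders reclassified = 6.9 × *f* × *q*; change in control response rate = 15 × *f* × *q* percentage points.

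| *f* | *q* | Control patients of 46 | Points |
|---|---|---|---|
| 0.10 | 0.05 | 0.03 | 0.08 |
| 0.30 | 0.20 | 0.41 | 0.9 |
| 0.50 | 0.40 | 1.38 | 3.0 |

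For scale, one reclassified patient is 1 / 46 = 2.2 points in that arm.

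**The case against.** The strongest reply is that the restriction is stated openly, in the same sentence as the aim, and is defensible. A non-measurable site cannot enter the sum of diameters, and calling it progressive is a judgement, which A1.5 gives to the treating physician, in an open-label trial. A1.5 also sets a high bar: worsening substantial enough to merit stopping therapy, with clear progression of a non-target lesion described as exceptional. A lesion that was progressing at entry need not meet that bar by week 9, and inclusion criterion 2 requires a best response of stable disease. All of this stands, and it is why the expected effect is small. It does not close the gap, because no other section restores the site in its non-target role.

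Four stronger readings are tempting and not supported:

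- *Every bone or bladder site is affected.* Section 9.1.1 gives these only as examples. A1.1 counts lytic or mixed bone lesions "as measurable lesions if the soft tissue component meets the definition of measurability", and nothing makes every bladder lesion non-measurable.
- *The analysis cannot show the impact at all.* It is informative wherever the site qualifies as a target.
- *The size is the number of patients with a non-measurable site.* At an assumed 20 to 40% that is 46 × 0.20 = 9.2 to 46 × 0.40 = 18.4 per arm, but these are patients whose two results coincide. Most would be non-responders, whose status cannot change.
- *It could tip the trial's decision.* The 0.68 boundary belongs to the principal analysis. Removing a control responder would also favour radiotherapy, so missed control events do not inflate the radiotherapy effect.

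The eCRF and the SAP are not available here, so the status of the site may already be captured, and section 15.2 lets the Trial Management Group add eCRF items without an amendment. That bears on the cost of the fix. The restriction itself is fixed in the protocol text.

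**Conclusion.** The point holds as a mismatch between the aim of the supplementary analysis and its definition. For patients whose planned site is not a target lesion, it equals the principal analysis by construction. How many such patients there will be is not stated. It may include some with a measurable site, if the A1.2 limits on target number are read as part of the target criteria.

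The missed effect runs one way, from responder to non-responder. It can arise in either arm, more plausibly among controls, whose site is not irradiated. Under the assumed ranges it amounts to about 0.03 to 1.4 of 46 control patients, or 0.08 to 3.0 points of control response rate. Both ranges are illustrations, not estimates. The primary analysis is unaffected and no decision rule uses the supplementary result, so this is a low-cost improvement of small expected effect.

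**What to change.** In section 12.4, define the supplementary analysis so that the planned site enters as a target lesion where it qualifies and otherwise as a non-target lesion under A1.5 and A1.6. On the dedicated eCRF, if not already captured, note the presence of the site at baseline and record its non-target status at week 9 (absent, present, unequivocal progression).

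Failing that, limit the stated aim in section 12.4 to planned sites that meet target-lesion criteria, and report how many patients per arm have a site that does not.

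Cost: one clause in section 12.4 and one eCRF status item, read from scans already taken. The drawback is that non-target progression is a more subjective reading than a diameter, which matters in an open-label trial. The blinded central review of objective responses already planned in section 12.4 covers the patients whose status could change, and could read this item for them.

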#### Secondary endpoints

Objective response rate according to iRECIST and clinical benefit according to RECIST v1.1 will be compared between trial arms as per the primary endpoint. Best response will be tabulated according to trial arm.

Duration of response, time to progression, progression free survival and overall survival will be presented according to trial arm using Kaplan-Meier survival plots and analysed using log-rank tests and Cox proportional hazards models. Rates of progression free and overall survival will be estimated at 12 and 24 months.

Treatment-related toxicity will be presented according to grade and trial arm.

Quality of life data will be analysed using standard algorithms to derive scores and handle missing data according to the questionnaire's scoring manual. The primary outcome measure for patient reported quality of life will be overall quality of life measured by the EORTC QLQ-C30 global health/quality of life subscale score, which will be treated as a continuous variable. Subscale scores will be compared between treatment groups at individual time points, as well as the change from baseline to Week 9 and 6 months, using ANCOVA adjusting for baseline scores. Additional analyses of EORTC QLQ-C30 subscales will dichotomise change in subscale scores from baseline to each follow-up timepoint according to whether or not patients have experienced a deterioration of >10 points, and compared between groups using chi-squared tests or Fisher's exact test, as appropriate. Analyses to account for the longitudinal nature of the data (generalised estimating equations) may also be used. Secondary QoL outcomes of interest include the EORTC QLQ-C30 subcales for physical functioning, role functioning and fatigue, individual domains and utility scores from the EQ-5D-5L.

QoL sub-study patients who are still being treated with atezolizumab at 12 months will be asked to complete the questionnaire at this timepoint. QoL data for this subset of patients will be compared with their baseline QoL data taking into account relevant covariates including other treatments taken, to explore the impact of long term use of atezolizumab on QoL.

Exploratory analyses will be conducted to investigate whether response varies according to site of target lesion. Details will be specified in the Statistical Analysis Plan.

Analyses of efficacy outcomes will be by intention-to-treat; safety analyses will be in the per protocol population.

Further details of analysis methods including definitions of analysis populations will be specified in a Statistical Analysis Plan in accordance with ICR-CTSU Standard Operating Procedures.

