**Exploratory objectives:** 

To correlate changes in biomarkers with toxicity, response to treatment and survival.

STUDY DESIGN Randomised controlled open label phase II trial with a group-sequential design.

TRIAL POPULATION Patients receiving atezolizumab for metastatic transitional cell carcinoma of the

urothelial tract.

RECRUITMENT TARGET 102 patients.

TREATMENT REGIMEN Atezolizumab +/- radiotherapy to the primary site or a metastatic lesion.

All participants will receive intravenous atezolizumab 1200mg three weekly until loss of clinical benefit or unmanageable toxicity up to a maximum of 2 years' treatment.

Radiotherapy (if allocated), 20Gy in 5 fractions. The first dose should be delivered during the first cycle of on study atezolizumab, starting on day 1 cycle 1 if possible. Target volume will be the investigator defined gross tumour volume (GTV) plus 0.5

cm. CTV plus 0.5 – 1.0 cm will be the planning target volume (PTV).

PRIMARY ENDPOINT Response at 9 weeks (RECIST v1.1)

SECONDARY ENDPOINTS Response according to iRECIST; clinical benefit at 9 weeks; best response up to 6

months; duration of response; time to progression; progression free survival; overall

survival; treatment related toxicity; patient reported quality of life.

EXPLORATORY ENDPOINTS

Molecular and pathological changes in response to atezolizumab +/- radiotherapy

[figure not shown]
FOLLOW UP Participants will have CT chest, abdomen and pelvis imaging every 9 weeks in the first

year and every 12 weeks in the second, or until RECIST v1.1 progression/iRECIST iCPD and treatment discontinuation. Following discontinuation of atezolizumab

participants will be assessed for disease status and survival every 3 months.

RE-ARM protocol IRAS 280335 / CCR5167

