# 2.2. Secondary objectives

Secondary objectives are to assess treatment related toxicity, response according to iRECIST, clinical benefit, progression-free survival, overall survival and patient reported quality of life.

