## 4.2. Secondary endpoints

- Response according to iRECIST
- Clinical benefit at 9 weeks after starting study treatment (CR/PR/SD according to RECIST v1.1)
- Best response up to 6 months according to RECIST v1.1 and iRECIST
- Duration of response
- Time to progression
- Progression free survival
- Overall survival
- Treatment related toxicity
- Patient reported quality of life, assessed using the EORTC QLQ-C30 (32) & EQ-5D-5L (33)

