#### 11.1.6. Serious Adverse Reaction (SAR)

A serious adverse reaction is an SAE that is suspected as having a causal relationship to the investigational medicinal product, as assessed by the investigator responsible for the care of the patient. A suspected causal relationship is defined as possibly, probably or definitely related (see definitions of causality table).

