# 11.2. Reporting adverse events to ICR-CTSU

Any toxicity, sign or symptom that occurs after commencement of study treatment and within 30 days of the last administration of study treatment, which is not unequivocally due to progression of disease, should be considered an AE. Out of range laboratory values should only be reported as AEs if they are clinically relevant (i.e. indicative of a clinical sign or symptom). The sign/symptom should be reported as the AE and the associated laboratory value provided as additional information where relevant.

All AEs must be reported on the relevant CRF and submitted to ICR-CTSU.

The severity of AEs should be graded according to CTCAE v5. For each AE, the highest grade observed since the last visit should be reported.

Whenever one or more toxicity/sign/symptom corresponds to a disease or a well-defined syndrome only the main disease/syndrome should be reported.

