#### 12.3.2. Secondary endpoints

- Objective response according to iRECIST (iCR + iPR)
- Clinical benefit at 9 weeks according to RECIST v1.1 (CR, PR, SD)
- Best response up to 6 months, defined as specified in A1.10
- Duration of response, defined as time from objective response until recurrence or progressive disease (PD)
- Time to progression, defined as time from randomisation until confirmation of progression
- Progression free survival, defined as time from randomisation until progression or death from any cause
- Overall survival, defined as time from randomisation until death from any cause
- Treatment related toxicity (CTCAE v5)

• Patient reported quality of life (assessed using the EORTC QLQ-C30 and EQ-5D-5L questionnaires) at 9 weeks and 6 months for all patients participating in the QoL substudy. In addition any QoL sub-study patients still being treated with atezolizumab at 12 months should be asked to complete the EORTC QLQ-C30 and EQ-5D-5L at this timepoint. The primary outcome measure will be overall quality of life, measured by the EORTC QLC-C30 qlobal health/QoL subscale score.

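### The only toxicity comparison by arm that the protocol specifies is limited to treatment-related events, so unblinded attribution could create or mask a radiotherapy effect

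*Protocol*

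**What the plan says.** The safety objective, endpoint and analysis all carry the same qualifier. Section 2.2 states: "Secondary objectives are to assess treatment related toxicity, response according to iRECIST, clinical benefit, progression-free survival, overall survival and patient reported quality of life". The endpoint list in section 4.2 gives "Treatment related toxicity", section 12.3.2 repeats it with CTCAE v5 grading, and section 12.4 says "Treatment-related toxicity will be presented according to grade and trial arm". No other comparison of toxicity by arm is specified.

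Data collection is wider than the analysis. Section 11.2 says "All AEs must be reported on the relevant CRF and submitted to ICR-CTSU". An event counts as an adverse event there unless it is plainly due to progression.

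The trial summary describes the design as: "Randomised controlled open label phase II trial with a group-sequential design". Sections 12.4 and A1.11 provide blinded central review for objective response, and A1.11 gives protection against reporting bias as the reason. No such review is described for toxicity.

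Relatedness has three reference points:
- Section 11.1.6: "A serious adverse reaction is an SAE that is suspected as having a causal relationship to the investigational medicinal product". Section 9 identifies that product as atezolizumab. The same definition leaves the judgement to the treating clinician: "as assessed by the investigator responsible for the care of the patient".
- Section 11.1.7: the causality scale is worded for trial treatment, which could include radiotherapy.
- Section 11.5: a list of events counts as expected if judged related to radiotherapy.

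**The concern.** Randomisation makes the arms comparable for every adverse event that occurs. It does not make them comparable for events that remain after someone who knows the allocation has decided which were caused by treatment.

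That decision differs between the arms by design. In the radiotherapy arm, fatigue, nausea, diarrhoea, colitis or shortness of breath has an additional recognised cause (section 11.5). In the control arm the same symptom can be put down only to atezolizumab, the disease or something else. Colitis and diarrhoea are also immune-related events of atezolizumab (sections 9.2.8 and 11.1.4), so the cause is ambiguous where both treatments are given. The bias could run either way. Awareness of radiotherapy may raise the share called related. If related is read as related to the investigational product, events put down to radiotherapy may drop out of the table.

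Section 1.5 makes a small effect on toxicity part of the conclusion the trial hopes to support. The measure chosen for that claim is the one most exposed to this bias.

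**Working it through.** The protocol states no toxicity rate and no attribution rate, so there is no figure to reproduce. The check has two parts.

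**Reading the sections together.** The qualifier appears in 2.2, 4.2, 12.3.2 and 12.4, so it is a choice of measure and not a slip in one sentence. Blinding of attribution is described nowhere. For serious events the treating investigator judges causality (11.1.6). The Chief Investigator's second assessment cannot lower that judgement and is not described as blinded (11.4). For non-serious events no assessor is named.

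**Size, with assumed inputs.** Let p be the true proportion of patients with a given event and a the probability that it is called related. The table then shows p × a in each arm, and the displayed difference, radiotherapy minus control, is

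p(RT) × a(RT) − p(C) × a(C).

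*False excess.* With equal true rates this reduces to p × [a(RT) − a(C)]. Take 50% attributed in control:

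| True rate, both arms | Control shown | RT shown, 60% attributed | RT shown, 70% attributed | RT shown, 80% attributed |
|---|---|---|---|---|
| 30% | 15% | 18% (+3) | 21% (+6) | 24% (+9) |
| 50% | 25% | 30% (+5) | 35% (+10) | 40% (+15) |
| 70% | 35% | 42% (+7) | 49% (+14) | 56% (+21) |

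For the 50% row, 0.50 × 0.50 = 0.25 in control, against 0.50 × 0.60 = 0.30 up to 0.50 × 0.80 = 0.40. With 51 patients per arm (section 5.1), 10 points is about 5 patients (51 × 0.10 = 5.1).

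*Masked excess.* Take true rates of 40% in control and 55% with radiotherapy, a real excess of 15 points, and 60% attributed in control:
- control shows 0.40 × 0.60 = 24.0%;
- radiotherapy at 60% attributed shows 0.55 × 0.60 = 33.0%, a difference of 9.0 points;
- at 50% attributed, 0.55 × 0.50 = 27.5%, a difference of 3.5 points;
- at 44% attributed, 0.55 × 0.44 = 24.2%, a difference of 0.2 points.

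Exact masking requires a(RT)/a(C) = p(C)/p(RT) = 0.40/0.55 = 0.727, that is a(RT) = 0.727 × 0.60 = 0.436. A wider imbalance overshoots. True rates of 30% v 39% with 60% v 30% attributed show 18.0% v 11.7%, so a real 9-point excess appears as a deficit of 6.3 points.

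*All reported events.* Counting events regardless of attribution to treatment sets a = 1 in both arms. The first example then shows a difference of 0 and the second shows 15 points, apart from the exclusion of progression-related events in section 11.2.

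**The case against.** **All-cause tables may be planned.** A reader might infer that the protocol rules out an all-cause comparison. It does not. Section 12.4 says what will be presented, not what will be left out, and it defers further detail to a statistical analysis plan in which such tables would be ordinary content. This limits the finding but does not remove it, because the protocol itself fixes the endpoint as treatment-related.

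**Other safety information is unfiltered.** The trial summary's objective speaks of toxicity without the qualifier, the monitoring committee reviews accumulating toxicity data (12.5), and serious events and events of special interest are reported without a causality filter (11.3). None of these specifies an all-cause comparison by arm. The QLQ-C30 comparison in 12.4 includes fatigue and needs no attribution, but it is a voluntary sub-study at fixed time points and does not capture worst grade.

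**The mechanism is assumed.** Both arms receive atezolizumab, so control-arm events can also be called related. The threshold is low, since a possible link is enough under 11.1.6. This makes very large imbalances less plausible. It is also tempting to say that the treating investigator attributes every event, but the protocol says so only for serious ones. For the rest, one can say only that the trial is open label and no blinding is described.

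**The remedy is not free of attribution.** Section 11.2 does not collect events whatever their cause. It excludes those clearly due to progression, which is itself an unblinded judgement. The filter would be narrower, not absent.

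**No test depends on the table.** This is correct. The table is descriptive, and no threshold or decision rule uses it.

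**Conclusion.** The point stands as a minor weakness in the choice of safety measure. The only toxicity analysis by arm that the protocol specifies is filtered by an unblinded judgement, made under different conditions in the two arms and against a reference that changes between sections. Under the assumed inputs, a spurious excess of 5 to 15 points at a 50% true rate, or near-complete masking of a 15-point excess, is arithmetically possible. Those figures show what differing attribution could do. They do not predict what will happen, and they depend entirely on attribution shares for which the documents offer no source.

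The documents do not support the stronger inference that all-cause events will go unreported or that a safety signal would be missed. Adverse events are collected and graded, serious events are reported in full, and the committee's review is not restricted to related events. The weakness lies in which comparison will carry the conclusion on added toxicity.

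**What to change.** In sections 12.3.2 and 12.4, with 2.2 and 4.2 aligned:

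1. Make all reported adverse events, as defined in 11.2 and regardless of attribution to treatment, by worst CTCAE grade and arm, the main safety comparison.
2. Keep treatment-related toxicity as a supportive subset.
3. State whether related means related to atezolizumab, to radiotherapy or to either, and use that meaning consistently in section 11.

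The cost is one extra table and a few lines of text. The data are already collected and graded under 11.2. The exclusion of events clearly due to progression would remain and should be noted beside the table.
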